anticoagulation be reserved for patients with": 1) "non-valvular AF who present with a clear AF onset within 12 hours in the absence of recent stroke or transient ischemic attack (within 6 months)", and 2) "non-valvular AF and a CHADS2 score < 2 who present after 12 hours but within 48 hours of AF onset", and 3) "as an alternative to at least

3 weeks of therapeutic anticoagulation before cardioversion, TEE may be used to exclude cardiac thrombus".

As such, these recommendations will likely reduce the frequency of immediate cardioversions (in the emergency department), increase referrals for inpatient and outpatient TEEs, and increase hospital admissions. We propose a randomized control trial that will assess the utility of cardiac CT to improve patient access and timely care. The results of this study could have worldwide impact by improving patient quality of life and timely access to cardioversion.

Imaging to Rule Out LA Thrombus

Currently, TEE is considered the reference standard technique for the detection of intracardiac thrombus. Although the gold standard, a TEE-guided therapy is still associated with an embolic rate of 0.8%.⁹ TEE does have limitations which include: need for NPO x 6-8 hours, patient discomfort, potential complications associated with the procedure (infection, aspiration, perforation, bleeding, etc) or with sedation.¹⁰

Contrast enhanced ECG-gated cardiac CT (CCT) is a sensitive, noninvasive alternative method used to exclude of left atrial and LAA thrombus. CCT provides high spatial and good temporal resolution and its ability to detect thrombus has been evaluated.¹¹⁻¹⁵ CCT, compared to TEE, for the exclusion of thrombus in the LAA had a sensitivity and specificity of 100% and 99.3%, respectively (Table 1).¹⁶ A high sensitivity is needed to minimize risk of embolus, and if a thrombus is detected on CT, a confirmatory TEE may be performed or patients may receive anticoagulation. Some argue that the potential benefits of CT and its lower associated procedural risk, the risk:benefit ratio would still favour CT.

This research is novel because it will be the first to demonstrate in a RCT, that CT can be used as an alternative to TEE. More importantly, demonstrating that CT is cost-effective would be extremely attractive to all stakeholders given the growing financial burden of healthcare.

Hypothesis

- Primary Hypothesis: Compared to TEE, CCTA will:
 - 1. Reduce time to cardioversion for in-patients

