- Secondary Hypotheses: Compared to TEE, CCTA will:
 - 1. Reduce length of hospital or emergency room stay,
 - 2. Improve patient quality of life (QoL),
 - 3. Not increase adverse events (arterial embolism, procedural complications, bleeding),
 - 4. Have superior cost-effectiveness.

Study Objective

Overarching objective: To evaluate CCT as an alternative to TEE to expedite cardioversion, improve patient care and reduce hospital admissions for AF and atrial flutter.

- Primary Objective: To determine if CCT can reduce time to cardioversion for in-patients
- Secondary Objectives:
 - To determine if CCT can reduce length of stay (in-patient hospitalization and emergency department)
 - To determine if CCT improves patient QoL
 - o To determine if CCT is associated with fewer or more adverse events
 - To determine the specificity of CCT (in patients with filling defects and subsequent TEE)

Outcomes Measures

- 1. Time to cardioversion (Time from referral for imaging)
- 2. Hospital admission rate
- 3. Length of hospital stay (in-patient and emergency department stay)

- 4. QoL before cardioversion, at hospital discharge and at 30 days
- 5. Adverse events (embolic (arterial) event, procedural complication, major bleed (need definition))
 - a. Embolic arterial event
 - b. Procedural complication
 - c. All bleeding
 - d. Major bleeding
- 6. Operating characteristics (specificity, PPV) of CCT (subanalysis of patients receiving TEE after CCT)

Study Design

This randomized controlled trial will randomize patients undergoing cardioversion for AF or atrial flutter before 3 weeks of anticoagulation. This pilot (Vanguard) study will aim to demonstrate feasibility of enrolment and assist with final sample size calculation.

Inclusion Criteria

- Patients admitted to hospital or seen in the ED who require LA imaging prior to cardioversion
- Age ≥ 18 years old
- Able and willing to comply with the study procedures

Exclusion Criteria

- Indication for acute cardioversion (e.g. hemodynamic instability, acute coronary syndrome (ACS), or pulmonary edema)
- Unwillingness or inability to provide informed consent
- Contraindication to Cardiac CT
 - Severe renal insufficiency(GFR< 45ml/min)
 - Allergy to intravenous contrast agents
 - Contraindications to radiation exposure (for example, pregnancy)
 - Inability to perform 20-second breath-hold
- Contraindication to TEE
 - Unrepaired tracheoesophageal fistula
 - Esophageal obstruction or stricture

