 - Perforated hollow viscus
 - Poor airway control
 - Severe respiratory depression
 - Uncooperative, unsedated patient

Methods

Recruitment

Patients who meet the inclusion/exclusion criteria will be randomized to either the interventional arm (CCT) or standard of care (SOC) arm (TEE). Prior to randomization, written informed consent will be obtained from each patient. Patients will undergo imaging as per clinical routine and reports will be issued immediately.

TEE protocol

TEE will be performed as per clinical routine using multiple standard tomographic planes to rule-out LA/LAA thrombus. Echocardiographic analysis will include: LAA-emptying velocity, and grading the severity of LAA spontaneous ECHO. The severity of the SEC will be graded on a 4 point scale with 1 = minor homogeneous contrast enhancement, 2 = significant homogeneous contrast

enhancement, 3 = significant, dense, and inhomogeneous, slow-moving contrast, and 4 = dense slow-moving contrast.

Cardiac CT protocol

As per local protocol, a non-contrast enhanced prospective ECG-triggered image acquisition will be acquired. This will be followed by a contrast-enhanced prospective ECG-triggered will be acquired using a tri-phasic contrast protocols. Delayed CT images will be acquired 60 seconds after the initial contrast-enhanced CT scan.Cardiac CT image interpretation will be performed as per clinical routine. The LA and LAA will be assess for filling defects and characterized based upon attenuation values. If LA/LAA thrombus cannot be excluded, filling defects will be assessed on the delay images. Increases in attenuation would be consistent with pseudo-thrombus from 'slow flow' and 'incomplete opacification'. Areas where attenuation does not change significantly (persistent filling defect) will be diagnosed as thrombus. It will be recommended that patients with thrombus will undergo TEE.

Prevention of Bias

Enrolled patients will be processed through the usual clinical routine for patient booking and investigators will not influence timing of booking.

Duration of Follow-up

Patients will be followed for 30 days after cardioversion using electronic charts and telephone follow-up for QoL measures.

Sample Size Calculation

This pilot (Vanguard) study will aim to demonstrate feasibility of enrolment and assist with final sample size calculation.

Statistic Methods

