Patient clinical source documents will include patient hospital/clinic records, physician's and nurse's notes, appointment book, original laboratory reports, special assessment reports, signed informed consent forms. All personal health information collected will be kept confidential unless release is required by law. For audit purposes only, the Ottawa Health Science Network Research Ethics Board and the University of Ottawa Heart Institute may review the patients' medical records under the supervision of [name] and his staff. The Master list containing the patients' personal health information will be kept separate from the patient screening and enrollment logs. The Master List which links the patient with the independent study number will only be accessible by [name] and his staff. The master link and study files will be stored separately and securely.

All paper records will be stored in a locked filing cabinet and /or office. All electronic records, including the Master List, will be stored on a secure internal hospital server and password protected, again only accessible by [name] and his staff. No identifiable information will be stored on any mobile devices (laptops, USB keys, CDS, DVDs, etc). The Investigator must keep source documents as described above on file for 10 years after completion or discontinuation of the study. After that period of time the documents may be destroyed, according to local regulations.

Publication Policy

In accordance with standard editorial and ethical practice, the results of this study will be published or presented at congresses or scientific meetings. Patients will not be identifiable in any publications or presentations.

References

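### As written, embolic and bleeding events after discharge rest on chart review alone and may be under-counted in both arms; the call already planned should ask about them

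*Combined protocol and SAP*

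**What the plan says.** Follow-up is described in one sentence, under Duration of Follow-up: "Patients will be followed for 30 days after cardioversion using electronic charts and telephone follow-up for QoL measures". The telephone purpose it names matches item 4 of Outcomes Measures, "QoL before cardioversion, at hospital discharge and at 30 days". The first two of those time points come no later than discharge, so the call is naturally the 30-day one.

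Safety is a secondary objective. The secondary hypothesis for CCT is "Not increase adverse events (arterial embolism, procedural complications, bleeding"), with no margin. Item 5 of Outcomes Measures lists "Adverse events (embolic (arterial) event, procedural complication, major bleed (need definition")), then separates embolic events, procedural complications, all bleeding and major bleeding. It gives no method of collection.

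Under Data Handling and Record Keeping, "Patient clinical source documents will include patient hospital/clinic records" and other clinical paperwork. Records from outside hospitals and patient-reported events are not mentioned.

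**The concern.** A chart records an event only if the patient brought it to a provider whose records the chart contains. An embolic event treated at another hospital may leave no trace, and a minor bleed managed at home almost certainly leaves none. Outcome 5c counts all bleeding, so such bleeds belong to the outcome.

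Embolic events carry particular weight. Under Cardiac CT protocol, TEE is recommended only when CT shows thrombus, and item 6 of Outcomes Measures covers specificity and PPV, not sensitivity. A thrombus missed by CT would therefore show itself mainly as an embolic event after cardioversion.

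Equal under-counting in both arms leaves a risk ratio unchanged on average. It still shrinks the absolute difference and the number of events, so a real increase becomes harder to see. For a hypothesis of no increase, that error is in the favourable direction. The pilot is also meant to inform the final sample size, and under-counted rates would mislead any planning of safety outcomes.

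**Working it through.** The plan states no sample size, event count, capture rate or margin, so there is no figure of its own to reproduce. What follows is an illustration.

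**Inputs**
- Embolic rate p = 0.8%, from Imaging to Rule Out LA Thrombus: "a TEE-guided therapy is still associated with an embolic rate of 0.8"%. Using it as the true 30-day rate in both arms is an assumption.
- s = share of post-discharge events that the chart captures. Assumed 0.5 to 0.9.
- d = days in hospital after cardioversion. Assumed. In-hospital capture is taken as complete.
- F(d) = share of 30-day events that occur by day d. Either even timing, F = d/30, or early clustering, F = 0.3 × d/5 + 0.7 × d/30 for d up to 5.

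**Formula.** Captured fraction = F(d) + (1 − F(d)) × s. Recorded rate = p × captured fraction.

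**1. Under-counting common to both arms.** With discharge on the day of cardioversion, d = 0 and F = 0, so the captured fraction is s:
- s = 0.5: 0.8% × 0.5 = 0.40%
- s = 0.7: 0.8% × 0.7 = 0.56%
- s = 0.9: 0.8% × 0.9 = 0.72%

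The same fractions apply to any outcome. For all bleeding, where the documents give no rate, 10% to 50% of true events would go unrecorded at these values of s.

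**2. Effect on a true increase.** Suppose the true CCT rate were twice 0.8%, that is 1.6%. The true difference of 0.8 percentage points would be recorded as s × 0.8, or 0.40 to 0.72 points. The ratio would stay at 2.

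**3. Difference between arms.** With equal d in both arms, the captured fractions are identical and the recorded CCT:TEE ratio under equal true risk is exactly 1.00 at any s. For unequal d:

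| d, CCT v TEE | Even timing, s = 0.5 | Even, s = 0.9 | Early clustering, s = 0.5 | Early, s = 0.9 |
|---|---|---|---|---|
| 0 v 1 | 0.968 | 0.996 | 0.923 | 0.991 |
| 1 v 3 | 0.939 | 0.993 | 0.867 | 0.982 |
| 0 v 5 | 0.857 | 0.982 | 0.706 | 0.956 |

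Example, 1 v 3 days, even timing, s = 0.5: CCT 1/30 + (29/30) × 0.5 = 0.517; TEE 3/30 + (27/30) × 0.5 = 0.550; ratio 0.939.

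**4. Scale.** With an assumed 100 patients per arm and full capture, 100 × 0.008 = 0.8 embolic events are expected per arm, and the chance of none in an arm is 0.992^100 = 0.448. At s = 0.7 with same-day discharge these become 0.56 events and 0.9944^100 = 0.570.

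**5. After the fix.** With s = 1 in both arms, the captured fraction is 1 whatever the discharge day. The recorded rate is the true 0.8%, and the ratio is 1.00.

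**The case against.** **The sentence does not exclude event questions.** This stands. It names QoL as the purpose of the call, but no call script is shown, and the case report form and schedule of assessments mentioned under Data Handling and Record Keeping are not in the documents. Nor is the reach of the electronic chart described. So events may be missed; the documents do not show that they will be. If the call already covers events, the protocol only needs to say so.

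**A reader might infer a bias in favour of CCT.** The secondary hypothesis "Reduce length of hospital or emergency room stay" suggests that CCT patients spend more of the 30 days outside hospital, where capture is poorer. The documents do not support that step. The 30 days run from cardioversion, whereas the primary saving, "Time to cardioversion (Time from referral for imaging"), lies before that point. A shorter total stay need not mean a shorter stay after cardioversion, and with equal stay after cardioversion the ratio is exactly 1.00. A difference is possible, for example if fewer ED patients are admitted with CCT, but it is not stated. The net direction is also open. If only events after cardioversion count, those during the wait for imaging are left out, and that wait is expected to be longer with TEE. This would work against CCT.

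**This is a pilot.** At 0.8 expected embolic events per arm of 100, no useful embolic comparison is possible even with perfect capture. That also stands, and it moves the practical weight to all bleeding and to the rates carried forward into planning.

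**Conclusion.** The concern holds as a gap in ascertainment. On its plain reading, the plan collects embolic and bleeding events after discharge from charts alone, which may under-count them in both arms and eases a conclusion of no increase. Under assumed post-discharge capture of 50% to 90% and same-day discharge, a true 0.8% embolic rate would be recorded as 0.40% to 0.72%. Longer stay after cardioversion would reduce the loss. All bleeding is probably the outcome most exposed.

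Bias between arms is not established. It requires a difference in stay after cardioversion, and most of the illustrated ratios are close to 1 unless the gap is several days or events cluster early. Confidence is high that the plan states no active collection of events, and low on the size of the loss, because every capture, timing and stay figure is assumed. The primary outcome is unaffected. This should be changed, but it does not threaten the study.

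**What to change.** Amend the sentence under Duration of Follow-up so that the telephone contact collects adverse events as well as QoL, alongside the electronic chart, over the same 30 days. Then specify:

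- One fixed script, identical in both arms, asking about stroke, TIA or other arterial embolism, any bleeding, and any visit to another hospital or physician.
- A request for outside records after each positive answer.
- Events counted from either source, chart or call.
- Classification by existing study staff from records with the arm masked. The two procedures are openly different and no blinding is described, so self-reported events should not be classified with the arm known.

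The cost is a few questions in a call already planned and occasional record requests. The downsides are slightly longer calls, some self-reported minor bleeds to classify, and higher observed event rates in both arms.

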Statistical analyses will be performed using SAS and/or SPSS. Statistical significance will be defined as p<0.05. Continuous variables will be presented as means and standard deviations, and categorical variables will be presented as frequencies with percentages. To compare variables, the Wilcoxon rank sum or T-test will be used to compare continuous variables and Fisher's exact test for categorical variables. Costs will be calculated using Ontario Case Costing Initiative and the Ontario Schedule of Physician Fees and Benefits.

Randomization

Randomization will occur at time of referral for TEE and be performed using a random generator. Patients will be stratified according hospital location (CICU versus ward versus emergency department) and according to mode of cardioversion (electrical versus pharmacologic) and patient sex.

Ethical Considerations

The investigator will ensure that this study is conducted in full conformance with the principles of the "Declaration of Helsinki" or with the laws and regulations of the country in which the research is conducted, whichever affords the greater protection to the individual. The study will fully adhere to the principles outlined in "Guideline for Good Clinical Practice" ICH Tripartite Guideline or with local law if it affords greater protection to the patient. It is the responsibility of the investigator, or a person designated by the investigator to obtain signed informed consent from each patient prior to participating in this study after adequate explanation of the aims, methods, anticipated benefits, and potential hazards of the study. The investigator or designee will also explain that the patients are completely free to refuse to enter the study or to withdraw from it at any time, for any reason. If new safety information results in

significant changes in the risk/benefit assessment, the consent form will be reviewed and updated if necessary.

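### Time to cardioversion has no value and no follow-up window for in-patients who are never cardioverted, and the stated analysis has no rule for them or for patients deferred because of thrombus

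*Combined protocol and SAP*

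**What the plan says.** - **Objective and outcome.** The primary objective (Study Objective) is "To determine if CCT can reduce time to cardioversion for in-patients". Outcomes Measures, item 1, sets the start of the clock: "Time to cardioversion (Time from referral for imaging". The end event is cardioversion. No value is given for a patient in whom it does not occur.
- **Entry.** Under Randomization, "Randomization will occur at time of referral for TEE". This is before imaging, so thrombus status is unknown. The inclusion criterion is a need for left atrial imaging ahead of cardioversion. Study Design says that the trial "will randomize patients undergoing cardioversion for AF or atrial flutter before 3 weeks of anticoagulation".
- **Routes away from prompt cardioversion.** The background (Imaging to Rule Out LA Thrombus) allows a confirmatory TEE or anticoagulation after a CT thrombus. The Cardiac CT protocol recommends TEE. Ethical Considerations allows withdrawal at any time.
- **Follow-up.** Duration of Follow-up counts 30 days from cardioversion. Outcomes Measures, item 4, asks for "QoL before cardioversion, at hospital discharge and at 30 days".
- **Analysis.** Statistic Methods: "Continuous variables will be presented as means and standard deviations", and "the Wilcoxon rank sum or T-test will be used to compare continuous variables". Fisher's exact test is for categorical variables only. The documents mention no analysis set, intention-to-treat rule, censoring, missing-data rule or worst rank.
- **Purpose.** Study Design and Sample Size Calculation give the pilot's aims as feasibility of enrolment and help with the final sample size. No sample size is stated.

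**The concern.** A patient randomised at referral who is never cardioverted has no time to enter in either test. That patient also has no follow-up window and no defined date for the 30-day QoL measure. Since nothing else is specified, such patients fall out of the primary comparison because of an event after randomisation. If they leave while waiting, the longer-waiting arm loses more of them and loses its longest waits first.

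A patient deferred for weeks does have a time, but the plan does not say whether it counts. Entered as raw hours, a few such values can dominate a mean, an SD and a t-test. Two choices thus stay open until the data are seen: keep or drop, and which test. At stake are the reading of the primary comparison and the estimates that this pilot passes to the final trial.

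**Working it through.** The plan states no sample size, effect or SD, so there is no figure of its own to reproduce. Every input below is an assumption unless a source is given.

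**Inputs.** Exponential waits with means (CCT v TEE) of 24 v 48 h up to 120 v 168 h. Thrombus in a share p of both arms, 1% to 10%. A deferred patient's time is the ordinary wait plus D. D = 3 weeks = 504 h; the background names that interval for anticoagulation before cardioversion, not for thrombus found on imaging. Two-sided 0.05.

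**1. SD with deferred patients kept or dropped.** Variance per arm is mean² if dropped and mean² + p(1−p)D² if kept; average over the arms and take the root. The mean gap is unchanged, because both arms gain pD.
- 24 v 48 h: average mean² = (576 + 2,304)/2 = 1,440. At p = 10%, p(1−p)D² = 0.09 × 254,016 = 22,861. Ratio = √(24,301/1,440) = 4.1.
- 120 v 168 h: average mean² = (14,400 + 28,224)/2 = 21,312. At p = 1%, p(1−p)D² = 0.0099 × 254,016 = 2,515. Ratio = √(23,827/21,312) = 1.06, about 1.1.

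| Waits (h) | p = 1% | 2% | 5% | 10% |
|---|---|---|---|---|
| 24 v 48 | 1.7 | 2.1 | 3.1 | 4.1 |
| 72 v 144 | 1.1 | 1.2 | 1.4 | 1.7 |
| 120 v 168 | 1.1 | 1.1 | 1.3 | 1.4 |

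The t-test sample size scales with the square of the ratio, so by 1.1 to 17. With a 1-week deferral the ratio is only 1.0 to 1.7 (including 48 v 96 h).

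**2. Power by simulation, 50 per arm, p = 5%, D = 504 h.** The kept range runs from deferring every CT false positive (0.7%, from the 99.3% specificity in Table 1) to deferring none.

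| Waits (h) | t-test dropped | t-test kept | Rank-sum dropped | Rank-sum kept |
|---|---|---|---|---|
| 24 v 48 | 90% | 16–20% | 82% | 73–76% |
| 72 v 144 | 90% | 57–63% | 81% | 73–75% |
| 120 v 168 | 35% | 23–25% | 29% | 24–26% |

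**3. Dropping patients who leave while waiting.** With a leaving rate h equal in both arms, a share q of TEE patients leaves when h = q/((1−q) × TEE mean). The mean among those cardioverted is 1/(1/mean + h). At 24 v 48 h and q = 20%, h = 0.25/48. The TEE mean is 48/1.25 = 38.4 h and the CCT mean 48/2.25 = 21.3 h. The gap is 17.1 h instead of 24 h, 29% too small. At q = 5% and 10% it is 7% and 15% too small. Counting leavers at their leaving time as the end of the wait gives the same means, so it does not restore the gap.

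**4. What ranking last costs.** If a share d of both arms is ranked last, P(CCT sooner) − ½ is multiplied by (1−d)², so n is multiplied by 1/(1−d)⁴: 1.04, 1.08, 1.23 and 1.52 at d = 1%, 2%, 5% and 10%. For 1:2 exponential waits, P(CCT sooner) = 2/3. At 90% power, Noether's formula gives (1.960 + 1.282)²/(6 × (1/6)²), rounded up to 64 per arm, rising to 66, 69, 78 and 97.

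**The case against.** The strongest reply has four parts.

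- **The large figures need inputs that the documents do not supply.** This stands. The 3 weeks comes from background on anticoagulation before cardioversion. After a CT thrombus the trial text recommends TEE; anticoagulation appears as an option only in the background. With long waits or a short deferral the effect is small.
- **The plan already names a robust test.** This stands in part. By rank-sum, keeping rather than dropping deferred patients costs about 3 to 9 points of power at 5% thrombus. But the t-test is equally available, and no rank is defined for a patient without a time.
- **It is a pilot, and a significant p-value is not its stated aim.** This limits the harm but does not remove it: the pilot is meant to inform the final sample size, and mean and SD are the only planned summary of this outcome. That an SD would be carried forward is an inference; the documents do not say so.
- **Dropping deferred patients need not bias anything.** If deferral is unrelated to the wait, the mean gap among the rest is unbiased. The cost in step 3 arises only when patients leave while waiting.

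A reader might infer from Study Design that the trial enrols or analyses only patients who are actually cardioverted. The documents do not support that. The inclusion criterion is met before imaging, and no analysis set is stated. Equally, no sentence tells anyone to exclude a patient; the omission follows from having no value to enter.

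**Conclusion.** The concern holds as a gap in the outcome definition, the follow-up window and the analysis rule. A never-cardioverted in-patient has no outcome value, no follow-up window and no 30-day QoL date, and following the plan omits that patient because of a post-randomisation event. This rests on the text alone.

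The size is conditional. With a 3-week deferral, the kept-to-dropped SD ratio runs from about 1.1 (120 v 168 h, 1% thrombus) to 4.1 (24 v 48 h, 10%). At 50 per arm, 5% thrombus and 24 v 48 h, t-test power is about 90% dropped against 20% kept; rank-sum is about 82% against 76%. The waits, thrombus rates, deferral length and sample size are all assumed.

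A reader might go further and infer a false-positive problem or a reversed treatment effect. Neither is shown here. The main consequence is for the estimates used to plan the final trial. It should be fixed before outcome data are seen.

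**What to change.** **Statistic Methods.**
- Analyse all randomised in-patients as randomised. Measure time from randomisation (at referral) to first cardioversion, with a fixed 30-day horizon for everyone.
- Use one pre-specified rank-sum test. Keep deferred patients at their actual time. Rank last those not cardioverted by day 30, including deaths and spontaneous conversions.
- Add a sensitivity analysis that counts spontaneous conversion at its own time, described as time to the end of the wait and not as time to cardioversion.
- For withdrawal before cardioversion, use the censored form of the test (Gehan-Wilcoxon).
- Randomisation is "stratified according hospital location (CICU versus ward versus emergency department) and according to mode of cardioversion (electrical versus pharmacologic) and patient sex", which makes 2 × 2 × 2 = 8 in-patient cells. Stratify the test by location (CICU v ward) only, fixed in advance, with no cell-count rule applied after recruitment.
- Do not use the t-test for this outcome. Report medians and the proportion cardioverted by day 30 per arm. Plan the final trial from these and from the estimated probability that a CCT patient is cardioverted sooner.

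**Duration of Follow-up.** For patients not cardioverted, run chart review and the 30-day QoL call from randomisation.

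**Cost.** A few sentences and a little extra follow-up. The effect is no longer a mean difference in hours. With 1:2 waits and 50 per arm, power is about 73–76% at 5% thrombus and 64–67% at 10%, against about 77–83% for a rank-sum test that drops deferred patients. Ranking spontaneous conversion last treats it as a poor outcome, which is why the sensitivity analysis is needed. The alternative is no free gain: with 40% of TEE patients leaving by that route (24 v 48 h), counting it at its own time gives about 51% power, against 62% when ranked last.

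### If waits vary by day of referral, the unadjusted primary test gives up precision that the already recorded referral time could recover at no data cost.

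*Combined protocol and SAP*

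**What the plan says.** The primary objective (Study Objective) is "To determine if CCT can reduce time to cardioversion for in-patients". Item 1 of Outcomes Measures sets the clock: "Time to cardioversion (Time from referral for imaging".

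Under Randomization: "Randomization will occur at time of referral for TEE and be performed using a random generator". Strata are hospital location (three levels), mode of cardioversion and sex. Referral day or hour is not among them.

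Under Prevention of Bias: "Enrolled patients will be processed through the usual clinical routine for patient booking and investigators will not influence timing of booking". Under Recruitment: "Patients will undergo imaging as per clinical routine and reports will be issued immediately".

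Under Statistic Methods, "the Wilcoxon rank sum or T-test will be used to compare continuous variables", and "Statistical significance will be defined as p<0.05". No covariate or stratified analysis is described. The Sample Size Calculation section gives no number of patients, effect size, SD or power. It describes a pilot meant to show that enrolment is feasible and to help size the final trial.

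**The concern.** A service wait under routine booking may depend heavily on when the request arrives. If elective imaging runs mainly in weekday working hours, a Friday-evening referral waits over the weekend for reasons unrelated to the modality. The planned two-sample test uses the referral time only to compute the outcome, so any such variation stays in the residual.

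Two things would be at stake. One is the precision of the pilot's comparison, including its exposure to a chance imbalance in late-week referrals. The other is the variance information passed to the final trial, if that trial is to use an adjusted analysis.

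**Working it through.** **1. Status of the covariate.** The outcome clock starts at referral, so the referral date and time must be captured. Randomisation also takes place at referral, so the assigned arm cannot affect the value. It is a legitimate baseline covariate and needs no new data. The imaging date would not qualify, because it follows randomisation.

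**2. No figure to reproduce.** The plan states no sample size, power, effect or SD. Everything below rests on assumptions. The test is taken as two-sided at 0.05, since sidedness is not stated.

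**3. What a given R² is worth.** Let R² be the share of within-arm variance explained by referral timing. The residual SD is SD × √(1 − R²), so required N scales by (1 − R²). For an assumed standardised difference d = 0.5:

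- N per arm for 80% power = 2(1.96 + 0.842)² / 0.25 × (1 − R²) = 62.8 × (1 − R²), rounded up.
- Power = Φ(d√(n/2) / √(1 − R²) − 1.96). With n = 50 and R² = 0.2 this is Φ(2.5/0.894 − 1.96) = Φ(0.835) = 80%.

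| R² | N per arm, 80% power | Power, 25 per arm | Power, 50 per arm |
|---|---|---|---|
| 0 | 63 | 42% | 71% |
| 0.1 | 57 | 46% | 75% |
| 0.2 | 51 | 51% | 80% |
| 0.3 | 44 | 56% | 85% |
| 0.5 | 32 | 71% | 94% |

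**4. How large R² could be.** Simulations assumed imaging Monday-Friday 08-16 h in both arms, referrals spread evenly over the week, a queue with median 3-10 open hours (log-SD 0.5-1.1), an exponential post-imaging delay with mean 4 h, 40 per arm, and CCT cutting the queue by 40%. A Friday-Sunday indicator explained about 6-32% of rank variance. Since 1/(1 − 0.06) = 1.06 and 1/(1 − 0.32) = 1.47, an unadjusted analysis would need about 6-47% more patients for equal precision. Rank-ANCOVA gained about 1-15 power points over Wilcoxon. Examples are 26% to 36%, 48% to 58%, 34% to 41% and 53% to 59%.

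**5. Where the gain shrinks** (same opening hours and 40 per arm unless noted).

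| Setting | R² | Gain, power points |
|---|---|---|
| Queues of 20-30 open hours | 0.3-2.6% | 0-2 |
| Enrolment on weekdays, working hours only | 1-19% | about 0-4 |
| Enrolment on weekdays, any hour | 1-14% | 0-5 |
| CT around the clock, TEE weekdays only | not reported | 0-1 |
| Both around the clock | about 0 | about 0 |

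A different model with exponential queues and 50 per arm shows the same dependence on queue length. With mean queues of 12 h (TEE) and 4 h (CT), and hours to the next weekday slot as covariate, power rose from 56% (Wilcoxon) to 83% (rank-ANCOVA). With 36 h and 20 h and a coarser weekend/off-hours covariate, it went from 51% to 54%. The largest fall in that model was 1.6 points (t-test 32.9%, ANCOVA 31.3%, 25 per arm, 1,000 replicates), which is not material.

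**6. Validity.** With no arm effect, rejection was about 4-6% for adjusted and unadjusted tests alike.

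**7. Chance imbalance.** If 3/7 of referrals fall on Friday-Sunday, the SE of the between-arm difference in that share with 40 per arm is √(2 × 3/7 × 4/7 / 40) = 0.111. A difference of 15 percentage points or more then occurs in about 21% of trials. The unadjusted standard error already allows for this, so adjustment reduces noise and does not correct a bias.

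**The case against.** The strongest reply is that the premise is not in the documents. They say that booking is routine; they do not say that laboratories close at weekends, how long queues are, or when patients can be enrolled. A reader might infer that waits do depend on the day of the week and that power is therefore lost. The plan does not support that as fact. Written consent is required before randomisation, so enrolment may in practice be confined to weekdays, where the gain is small. This stands, and it is why the point is conditional.

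A reader might also infer that the pilot's SD is inflated. It is not, for an unadjusted final trial: weekly variation would recur there, and the unadjusted SD is the right one. It is too large only if the final trial is analysed with adjustment.

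Third, this is a feasibility pilot with no power target, so lost power is not a failure against a stated aim. That also stands. But the plan does set a significance threshold, and the pilot is meant to inform the final sample size, so knowing how much variance referral day explains is directly useful.

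Fourth, out-of-hours access may be part of how CCT shortens the wait, so weekend waiting in the TEE arm is not purely noise. Adjusting for a pre-randomisation day does not remove that benefit, but a single main effect would not display it. The descriptive table proposed below is needed for that.

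Finally, the declared stratification factors have a stronger claim to be in the model than referral day. That is accepted, and they belong in the fix.

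**Conclusion.** The point holds as a conditional, low-cost improvement in efficiency. The planned primary comparison leaves unused a baseline value that the trial must record and that could explain a useful share of the outcome. With 40 per arm and weekday-hours imaging, the benefit is about 1-15 power points when queues are short. It is about 0-5 points with long queues or weekday-only enrolment, and about zero with round-the-clock imaging. Adjustment was never materially harmful. The opening hours, queue lengths, arm size and effect behind these figures are all assumptions. The documents do not support a claim of bias, of an invalid test, or of a wrong SD for an unadjusted final trial.

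**What to change.** In Statistic Methods, before outcomes are seen, name one primary model: a rank-ANCOVA of time to cardioversion on arm, with referral day (Friday-Sunday versus Monday-Thursday, from the referral timestamp), hospital location, mode of cardioversion and sex as covariates. ANCOVA on log time is an acceptable alternative if an effect in ratio terms is preferred, but the plan should commit to one.

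Alongside it:
- report the unadjusted result;
- report the outcome variance with and without the covariates, on the scale to be used for sizing the final trial;
- tabulate waits by arm and referral period, descriptively, to show any difference in out-of-hours access.

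The cost is a short paragraph and five degrees of freedom: one for referral day and 2 + 1 + 1 = 4 for the stratification factors. No new data and no extra patients are needed.
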